9.5.1.1. Analysis of Primary Efficacy Endpoint

To assess the efficacy endpoint for the primary objective, preventing the first occurrence of RT-PCR confirmed protocol-defined ILI within the period of 14 days post study intervention through the end of the influenza season, Cox proportional hazards regression model will be used to estimate HR. The rVE, ie, 1-HR (mRNA-1010 vs. active comparator) will be estimated along with the 2-sided 95% CI and 1-sided *p-value* for testing $H_0^1: rVE \leq -10\%$.

The rVE is defined as the percent reduction in the hazard of the primary endpoint (mRNA-1010 vs. active comparator) and will be estimated using 1-HR estimand. A stratified Cox proportional hazard model with study intervention group as a fixed effect will be used based on the PP Set to estimate the HR (mRNA-1010 vs. active comparator). The stratification factors at randomization, ie, age group (≥ 50 to < 65 years or ≥ 65 years) and influenza vaccine status in the previous season (received or not received), will be applied as the strata variables. The Efron's method will be used to handle ties.

For the primary efficacy endpoint, participants without RT-PCR confirmed protocol-defined ILI will be censored at the last study assessment date. Potential intercurrent events may include:

1. Early discontinuation or death unrelated to influenza; or
2. Early ILI up to 14 days after study intervention.

In the estimand of the primary analysis on the primary endpoint, a hypothetical strategy will be used to address the intercurrent events in the primary analysis based on the PP Set. The details are presented in [Section 11.3](#).

Participants without RT-PCR confirmed protocol-defined ILI will be censored at Day 181 (Month 6) or end of influenza season (whichever occurs later), or at the date of early discontinuation or death unrelated to influenza, whichever is earlier. Participants with early RT-PCR confirmed protocol-defined ILI up to 14 days after the study vaccination will be censored at the start date of the early RT-PCR confirmed protocol-defined ILI (see [Section 11.6](#) for country-specific amendment affecting this paragraph).

The trial will be considered to meet the primary efficacy objective if the *p-value* for rejecting $H_0^1: rVE \leq -10\%$ is less than the nominal *p-value* based on the Lan-DeMets Pocock boundaries, on the PP Set. The nominal alpha at the IA and final analysis will be 2.07% at IA and 1.2% at final analysis.

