Analyses of the primary endpoint will be also performed based on the mITT Set using the same methods as described above.

To support the primary analysis, rVE will also be estimated by 1 minus the ratio of incidence rates adjusting for person-time, and the 95% CI of rVE will be computed using the exact method, conditional upon the total number of cases adjusting for person-time.

In addition, Kaplan Meier curve will be used to plot the estimated cumulative incidence rates over time by vaccine group. Participants without a case for the primary endpoint identified will be censored at Day 181/Month 6 or end of influenza season, whichever ends later.

Once the noninferiority of mRNA-1010 vs. active comparator is demonstrated using the PP Set, superiority of mRNA-1010 vs. active comparator will be evaluated using the same endpoint on the mITT Set, either at an IA or at the final analysis.

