6.3.1.2. Analysis of the Primary Efficacy Endpoint

6.3.1.2.1. Primary Analysis for Noninferiority

The primary analysis for NI will first be performed based on the PP Set. The NI hypotheses testing is presented in [Section 4.2.1](#).

To assess the efficacy endpoint for the primary objective, preventing the first occurrence of RT-PCR confirmed protocol-defined ILI within the period of 14 days post study intervention through the end of the influenza season, Cox proportional hazards regression model will be used to estimate HR. The rVE, i.e., 1-HR (mRNA-1010 vs. active comparator) will be estimated along with the 2-sided 95% confidence interval (CI) and one-sided p-value for testing $H_0^1: rVE \leq -10\%$.

The number and percentage of participants who had a case for the primary efficacy endpoint will be summarized by vaccination group. The symptoms associated with the first RT-PCR confirmed protocol-defined ILI will be summarized by number and percentage of participants with each symptom by vaccination group.

A stratified Cox proportional hazard model including study vaccination group as a fixed effect will be used to estimate the HR (mRNA-1010 vs. active comparator) based on the PP Set. The stratification factors at randomization, i.e. age group (≥ 50 to < 65 years or ≥ 65

years) and influenza vaccine status in the previous season (received or not received), will be applied as the strata variables. Efron's method will be used to handle ties. The rVE will be estimated along with the two-sided 95% CI and one-sided p-value for testing $H_0^1: rVE \leq -10\%$ (inferior).

Potential intercurrent events may include:

1. Early discontinuation or death unrelated to influenza; or
2. Early ILI up to 14 days after study vaccination.

In the estimand of the primary endpoint, a hypothetical strategy will be used to address the intercurrent events in the primary analysis based on the PP Set. The censoring rules for the occurrence of ILIs are presented in [Appendix I](#).

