Participants without RT-PCR confirmed protocol-defined ILI will be censored at Day 181 (Month 6) or the end of the influenza season (whichever occurs later), or at the data cutoff date for interim analysis, or at the date of early discontinuation or death unrelated to influenza, whichever is earliest. Participants with early RT-PCR confirmed protocol-defined ILI up to 14 days after the study vaccination (i.e., start date of the RT-PCR confirmed ILI \leq vaccination date +13) will be censored at the start date of the early RT-PCR confirmed protocol-defined ILI.

The trial will be considered to meet the primary efficacy objective by demonstrating NI of mRNA-1010 to the active comparator if the one-sided p-value for rejecting $H_0^1: HR \geq 1.1$ (equivalently, $H_0^1: rVE \leq -10\%$) is less than the nominal alpha based on the Lan-DeMets Pocock approximation spending function, based on the PP Set. The nominal one-sided alpha level will be 2.07% at IA, and 1.2% at the final analysis, respectively, if the IA is conducted when exactly 75% of the total number of cases are observed.

As sensitivity analyses, the primary endpoint analysis for NI will be repeated on the mITT Set using the same methods as described above. The NI analysis of the primary efficacy endpoint will also be performed using the actual stratification factors (CRF derived) on the PPS Set.

Thirdly, the NI analysis will be repeated on the PP Set with co-infected cases excluded from the analyses:

- co-infection of influenza with COVID-19 and/or respiratory syncytial virus (RSV) as confirmed by the RT-PCR respiratory test panel;
- co-infection of influenza with any other respiratory virus as confirmed by the RT-PCR respiratory test panel.

Co-infections are identified from the same NP swab or two swabs collected within 3 days.

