6.3.1.2.2. Primary Analysis for Superiority

If the NI of mRNA-1010 vs. active comparator is demonstrated using the PP Set, superiority of mRNA-1010 vs. active comparator will be evaluated using the same primary endpoint based on the mITT Set, either at IA or at the final analysis.

Superiority of mRNA-1010 vs. the active comparator on the primary efficacy endpoint will be concluded if the one-sided p-value for rejecting $H_0^2: HR \geq 1$ (equivalently, $H_0^2: rVE \leq 0\%$) is less than the nominal alpha based on the Lan-DeMets Pocock approximation spending function, based on the mITT Set. For this superiority testing, the nominal one-sided alpha level will be 2.07% at IA, and 1.20% at the final analysis, respectively, if the IA is conducted when exactly 75% of total number of cases are observed.

As for the primary NI analysis, the following sensitivity analyses for the primary superiority analysis will be conducted: 1) the superiority analysis will be repeated on the PP Set using the same methods as described above; 2) the superiority analysis of the primary efficacy endpoint will also be performed using the actual stratification factors (CRF-derived) on the mITT Set; 3) the superiority analyses will be performed on the mITT Set by excluding RT-PCR confirmed protocol-defined ILI co-infected with other respiratory viruses as confirmed by RT-PCR respiratory test panel (see Section 6.3.1.2.1).

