6.3.1.2.3. Supportive Analyses

As a supportive analysis, rVE will be estimated by one minus the ratio of incidence rates (mRNA-1010 vs. active comparator) multiplied by 100%:

$$rVE = 100 \times (1 - \text{ratio of incidence rates adjusting for person-time}) \%$$

The 95% CI of rVE will be computed using the exact method conditional upon the total number of cases adjusted by the total person-time.

For each participant, the person-time is calculated as the time (days) from randomization to the date of the first episode for participants with a case, and the time (days) from randomization to the date of censoring for participants without a case (or who are censored). Then each participant's person time is adjusted by 180 days to obtain person-season, i.e.

$$\text{person-season} = \text{person-time} / 180.$$

The total number of person-seasons for each vaccination group is the sum of the individual person-seasons in the vaccination group.

The incidence rate per 1000 person-seasons for each vaccination group will be calculated as the number of participants with a case (i.e., first episode of RT-PCR confirmed protocol-defined ILI at least 14 days post vaccination and up to Day 181 (Month 6) or end of the influenza season, whichever occurs later) divided by the total person-season in each vaccination group multiplied by 1000. The same censoring rules as described for the primary analyses will be followed.

Summaries of total person-season and incidence rate, and 95% CI for incidence rate, will be provided by vaccination group. The 95% CI of the incidence rate will be calculated using the exact method (Poisson regression) and adjusted by person-time.

A stratified log-rank test will be performed to assess the time to first episode of RT-PCR confirmed protocol-defined ILI starting 14 days post vaccination up to Day 181 or at the end of the influenza season.

A Kaplan-Meier curve will be used to plot the estimated cumulative incidence rates over time by vaccination group. Cases of RT-PCR confirmed protocol-defined ILI will be counted starting 14 days post vaccination up to Day 181 or at the end of the influenza season, whichever occurs later. The same censoring rules as described for the primary analyses will be followed.

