6.5. Planned Analyses

There is one planned IA with data cut-off around the middle of February 2023 regardless of number of influenza cases accrued for the primary NI hypothesis to be tested to support the primary objective. The intent of the IA is for early detection of reliable evidence that rVE of mRNA-1010 is noninferior to the active comparator. The Lan-DeMets Pocock boundaries are used for calculating efficacy boundaries and to preserve the (1-sided) 2.5% Type I error rate over the IA and the final analysis (when the target number of cases have been observed), relative to the hypothesis:

$$H_0^1: HR \geq 1.1 \text{ (equivalently, rVE} \leq -10\%).$$

If NI is demonstrated at an IA, the subsequent final analysis will be considered supportive in nature for the NI claim. The DSMB will review the IA results and make recommendations to the Sponsor in terms of study results reporting and unblinding based on the boundaries of early efficacy as described in this section.

In summary, one IA for the primary efficacy endpoints and a final efficacy analysis are planned in this study ([Table 4](#)). An EoS analysis may be performed in this study as described below.

- IA for the primary efficacy endpoint will be performed with data cut-off around the middle of February 2023 when it is projected that approximately 75% of the total cases (274 RT-PCR confirmed protocol-defined ILI cases across both treatment groups) would be observed in the PP Set. In the case that fewer cases are observed by middle of February, the IA will continue to be conducted during this timeframe due to seasonality considerations. The nominal alpha level to be spent at the IA and final analysis will be adjusted accordingly. The DSMB will review the unblinded IA results.
- The final efficacy analysis will be performed when approximately 365 cases across both treatment groups have been observed in the PP set.
- The EoS analysis may be performed when all study participants have completed the final visit on Day 361 (Month 12) or have withdrawn from the study. The study database will be cleaned and locked, and the study will be unblinded.

The RT-PCR confirmed ILI cases are counted when the first episode starts 14 days after the vaccination and up to Day 181/ Month 6 or at the end of the influenza season whichever ends later.

Table 4: Planned Analyses and Hypothesis Testing for the Primary Efficacy Endpoint

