6.5.1. Interim Analysis

There is one planned IA at 75% of total target cases across the 2 treatment groups and a final analysis for the first null hypothesis to be tested to support the primary objective. The main intent of the IA is for early detection of reliable evidence that rVE of mRNA-1010 is noninferior to the active comparator. The Lan-DeMets Pocock approximation spending function is used for calculating efficacy boundaries and to preserve the (one-sided) 2.5% Type I error rate over the IAs and the final analysis (when the target number of cases have been observed).

The NI hypotheses are as follows:

Null hypothesis: $H_0^1: rVE \leq -10\%$ (inferior)

Alternative hypothesis: $H_a^1: rVE > -10\%$ (non-inferior)

Equivalently, the NI hypotheses are:

$H_0^1: HR \geq 1.1$ (inferior)

$H_a^1: HR < 1.1$ (non-inferior)

If NI is demonstrated at an IA, the subsequent analyses will be considered supportive in nature for the NI claim. The DSMB will review the IA results and make recommendations to the Sponsor in terms of study results reporting and unblinding based on the boundaries of early efficacy as described in this section, safety data, and data external to this study.

[Table 5](#) summarizes the timing, number of cases, and decision guidance at each IA and final analysis.

Table 5: Interim Boundaries Using Lan-DeMets Pocock Spending Function, Calculation Based on the PP Set for the Endpoint Supporting the Primary Objective

| Information Fraction (% of total #cases) | Number of Cases | Nominal Alpha (1-sided) \pm | Efficacy Boundary Rejecting H_0 : $rVE \leq -10\%$ | Cumulative Probability (Crossing Efficacy Boundary if the True $rVE = 25\%$) |
|--|-----------------|-------------------------------|--|---|
| IA (75%) | 274 | 2.07% | $rVE \geq 14.0\%$ ($HR \leq 0.860$) | 78.9% |
| Final Analysis (100%) | 365 | 1.2% | $rVE \geq 13.2\%$ ($HR \leq 0.868$) | 95.0% |

\pm : a actual nominal alpha may be adjusted based on the actual information fraction at individual IA(s).

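### The primary rVE is reported with a fixed 95% CI that does not match the nominal alphas (2.07% interim, 1.2% final), so the interval can exclude the null value beside a failed test

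*SAP*

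**What the plan says.** For the primary noninferiority (NI) analysis on the PP Set, SAP 6.3.1.2.1 states: "The rVE will be estimated along with the two-sided 95% CI and one-sided p-value for testing" the null hypothesis of rVE at or below −10%. Protocol 9.5.1.1 agrees: the rVE "will be estimated along with the 2-sided 95% CI and 1-sided" p-value.

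The success rule uses other levels. For NI, SAP 6.3.1.2.1 says "The nominal one-sided alpha level will be 2.07% at IA, and 1.2% at the final analysis, respectively", provided the IA is at exactly 75% of cases. SAP 6.3.1.2.2 sets the same levels for superiority on the mITT Set: "the nominal one-sided alpha level will be 2.07% at IA, and 1.20% at the final analysis, respectively".

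Four further points bear on this:

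- SAP 6.3.1.2.2 names no confidence interval for superiority. A 95% level is inferred from Protocol 9.5.1.1: "Analyses of the primary endpoint will be also performed based on the mITT Set using the same methods as described above".
- The supportive interval in SAP 6.3.1.2.3 is also at 95%: "The 95% CI of rVE will be computed using the exact method conditional upon the total number of cases", adjusted for person-time.
- SAP 6.5 sets the IA by calendar, with "data cut-off around the middle of February 2023 regardless of number of influenza cases accrued", so the nominal alphas may move from 2.07% and 1.2%.
- SAP Table 5 prints success boundaries on the rVE scale, but its title limits them: "Calculation Based on the PP Set for the Endpoint Supporting the Primary Objective". No such boundary is printed for superiority.

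Neither document plans an interval at the nominal alpha or says that the 95% interval is descriptive only.

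**The concern.** A reader expects a confidence interval for a confirmatory endpoint to agree with its test. Here the lower 95% limit is a one-sided 2.5% statement at each look, while the test is stricter at both looks and markedly so at the final one. The mismatch runs one way: whenever the test passes, the 95% interval excludes the null value, but the interval can also exclude it when the test fails. A report could then show a relative efficacy interval wholly above 0% (or above −10%) next to a conclusion that superiority (or NI) was not shown.

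Superiority is the more exposed case. It is tested again at the final analysis even if NI was shown at the IA, whereas the final-look NI conflict is moot once NI has been shown at the IA. Superiority also lacks a printed rVE boundary.

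The key secondary endpoints are not affected. SAP 6.3.2.2.1 and 6.3.2.2.2 test them once, at the final analysis, at one-sided 2.5%, which a 95% interval matches.

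**Working it through.** **Inputs.** Overall one-sided alpha 2.5%, 1:1 allocation, NI margin HR 1.1 and target rVE 25% (HR 0.75), from SAP 4.2.1 and 4.3. Cases at IA and final: 274 and 365 (PP Set), 290 and 386 (mITT Set), from SAP Table 4.

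**Assumptions.** SE(log HR) = 2/√d for d cases; Pocock-type spending 0.025 × ln(1 + (e − 1)t) at information fraction t; correlation √t between the looks. The requirement that NI pass first is not modelled for superiority.

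**Reproducing the plan.** At t = 0.75 the alpha spent at the IA is 2.07% (z = 2.040). Solving the bivariate normal for the final look gives 1.197%, that is 1.2% (z = 2.258). The NI boundaries are:

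- IA: 1.1 × exp(−2.040 × 2/√274) = 0.860
- Final: 1.1 × exp(−2.258 × 2/√365) = 0.868

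Both match SAP Table 5. Power is 93.7% for NI (Protocol Table 8: 93.7%) and 76.4% for superiority (SAP 4.3: about 76%).

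**Where interval and test disagree.** The 95% interval excludes the null HR0 when the observed HR is below HR0 × exp(−1.960 × 2/√d). The test uses 2.040 or 2.258 in place of 1.960.

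| Look and hypothesis | Cases | Test passes at HR ≤ | 95% CI excludes null at HR < | Discordant observed rVE |
|---|---|---|---|---|
| IA, NI | 274 | 0.860 | 0.868 | 13.2% to 14.0% |
| IA, superiority | 290 | 0.787 | 0.794 | 20.6% to 21.3% |
| Final, NI | 365 | 0.868 | 0.896 | 10.4% to 13.2% |
| Final, superiority | 386 | 0.795 | 0.819 | 18.1% to 20.5% |

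**Examples at the final look.**

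- Superiority, observed rVE 19% (HR 0.81): SE = 2/√386 = 0.1018, z = ln(0.81)/0.1018 = −2.07, p = 1.92%, which fails 1.2%. The 95% CI is 1.1% to 33.7%; the 97.6% CI is −1.9% to 35.6%.
- NI, observed rVE 12% (HR 0.88): SE = 2/√365 = 0.1047, z = ln(0.88/1.1)/0.1047 = −2.13, p = 1.65%, which fails 1.2%. The 95% CI is −8.0% to 28.3%; the 97.6% CI is −11.5% to 30.5%.

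**How often, at true rVE 25%.** The final-look figure is the probability of missing the IA boundary and then having 1.960 < Z < the final boundary.

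| IA timing | Final look, NI | Final look, superiority | Given hypothesis still open, NI | Given still open, superiority |
|---|---|---|---|---|
| 50% | 2.3% | 6.1% | 6.9% | 10.8% |
| 60% | 2.5% | 6.4% | 10.6% | 13.7% |
| 75% | 2.4% | 6.1% | 18.2% | 17.7% |
| 90% | 1.6% | 4.2% | 23.4% | 17.2% |

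At the IA itself the probability of discordance is 1.6% (NI) and 2.9% (superiority) with a 75% IA, and 6.8% and 7.8% with a 50% IA.

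**Matched levels, 1 − 2 × nominal alpha.** 95.86% (IA) and 97.6% (final) for an IA at 75%; 96.9% and 97.2% at 50%; 95.3% and 97.5% at 90%.

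**The case against.** The strongest reply is that there is no inferential defect. Every success rule in both documents is a p-value against the nominal alpha, no interval decides anything, and a 95% interval for estimation beside a group-sequential p-value is a common choice. The p-value is reported next to the interval, and its threshold is stated in the same subsection. For NI, the rVE boundaries are also printed. For superiority, the 95% level is only inferred. On this view a label on the 95% interval would be enough.

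Much of this stands. Error rate and power are untouched, NI is partly covered by the printed boundaries, and for superiority the firm statement is that the plan does not give the interval level. If the 95% interval were misread as the decision rule, the one-sided error would be about 3.4% (final look only) or 3.7% (both looks), but the plan contains no such rule.

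The reply does not remove the mismatch. The label it relies on is absent, and superiority has neither a printed boundary nor a stated interval level. SAP 6.6 also refers to significance at 2.5% when describing how the testing sequence continues. Read alone, that could make p = 1.92% with an interval above zero look like a success, although the nominal-alpha rule in the same section governs. Looking only at the final analysis would understate the issue, since an early IA makes discordance at the IA more likely than at the final look.

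**Conclusion.** The concern holds as a reporting issue that should be corrected. The planned 95% interval for the primary rVE is not at the level tested at either look. With the IA at 75%, the final-look discordant bands are rVE 10.4% to 13.2% for NI and 18.1% to 20.5% for superiority. At the target rVE of 25% such a final result has probability 2.4% and 6.1%, or about 18% for each among trials in which that hypothesis is still open. The tests, sample size, power and overall one-sided 2.5% error are unaffected.

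These figures rest on the log-HR variance 4/d and the planned case numbers, so the fitted Cox standard errors will shift the bands slightly. The superiority figures also assume that its interval would be at 95%, which the SAP does not state.

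**What to change.** In SAP 6.3.1.2.1, add a sentence that the confidence interval for the primary rVE is reported at level 1 − 2 × the nominal one-sided alpha actually used at that look: 95.86% at the IA and 97.6% at the final analysis if the IA is at exactly 75%, otherwise recalculated from the realised information fraction. In SAP 6.3.1.2.2, state that the same rule applies to the superiority analysis on the mITT Set. Keep the 95% interval, labelled as descriptive and not used for the success decision. Leave the key secondary endpoints as they are.

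The cost is those two sentences and a changed confidence level in the Cox output. The matched interval is wider on the log-HR scale by 2.040/1.960 = 1.04 (4%) at the IA and 2.257/1.960 = 1.15 (15%) at the final look, taking z = 2.257 for the rounded 1.2%. Prespecifying it before unblinding avoids having to choose or explain an interval once the result is known.
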